2.0 DEFINITIONS

Term/Abbreviation	Definition
Carbon-13	Carbon-13, denoted as ^{13}C , is a stable, non-radioactive , safe, naturally occurring form of carbon. Carbon-13 occurs in nature in a natural abundance of approximately 1%.
Carbon-12	Carbon-12 (^{12}C) is the most abundant, non-radioactive form of carbon in nature. Natural abundance is approximately 99%.
ABCA GIRMS	Automated Carbon Breath Analyzer Gas Isotope Ratio Mass Spectrometer. Used to analyze stable, non-radioactive isotopes of carbon, ^{13}C and ^{12}C , in QC gases and human breath samples. The ABCA GIRMS is an FDA-approved instrument for use with Cairn Diagnostics' ^{13}C -Spirulina Gastric Emptying Breath Test ("GEBT"). For these purposes, the instrument measures the ratio of $^{13}\text{CO}_2/^{12}\text{CO}_2$ in QC gases and human breath.
AE	Adverse Event
Delta values ($\delta^{13}\text{C}$)	Amount of ^{13}C in a sample expressed as a ratio of carbon-13 to carbon-12: $\delta^{13}\text{C}(\%) = \frac{R_B - R_S}{R_S} * 1000$ Where R_B is the ratio of $^{13}\text{C}/^{12}\text{C}$ of the sample and R_S is the ratio of $^{13}\text{C}/^{12}\text{C}$ in Pee Dee Belemnite (PDB), the reference standard for these measurements.
DOB	Delta Over Baseline i.e. the difference in delta value at any given time point and the pre-meal/baseline delta value

Term/Abbreviation	Definition
GEBT	Gastric Emptying Breath Test. The ^{13}C -Spirulina Gastric Emptying Breath Test ("GEBT") is an FDA-PMA approved, Class III combination drug medical device in vitro diagnostic product intended for measurements of the rate of solid phase gastric emptying and identification of gastroparesis (delayed gastric emptying).
GES	Gastric Emptying Scintigraphy
PHI	Personal Health Information
SAE	Serious Adverse Event

3.0 BACKGROUND

3.1 Intended Use

The Gastric Emptying Breath Test (GEBT), to be used with the GEBT test meal, is a quantitative test intended for use in the measurement of the rate of gastric emptying of solids and to aid in the diagnosis of delayed gastric emptying (gastroparesis) in adults who are symptomatic for gastroparesis. For these purposes, the test system utilizes a Gas Isotope Ratio Mass Spectrometer (GIRMS) for the measurement of the ratio of $^{13}\text{CO}_2$ to $^{12}\text{CO}_2$ in breath samples.

The GEBT should be administered under supervision of a health care professional although no specialized facilities or specially licensed personnel are required.

3.2 Principle of the GEBT

After an overnight fast, a test meal containing non-radioactive ^{13}C -labeled Spirulina is administered to the patient. As the test meal is emptied from the stomach it is rapidly absorbed across the duodenum and metabolized giving rise to exogenous ^{13}C -labeled CO_2 which is excreted in the breath. The rate of $^{13}\text{CO}_2$ excretion in breath at any given GEBT measurement time is directly proportional to the rate of gastric emptying.

3.3 Description of the GEBT Device

Cairn's ^{13}C -Spirulina GEBT is a Class III in vitro diagnostic medical device that consists of three FDA regulated components:

- A diagnostic drug (^{13}C -Spirulina/Egg mix) that contains the active pharmaceutical ingredient (^{13}C -Spirulina) that gives rise to ^{13}C -labeled CO_2 in patients' breath when taking the test.
- A kit containing the diagnostic drug, repackaged saltine crackers, consumables used to prepare the meal, a breath collection kit (screw capped glass tubes and a straw), materials to allow return of breath samples and approved labeling (instructions for use/package insert).
- An Automated Breath Carbon Analyzer Gas Isotope Ratio Mass Spectrometer (ABC-A-GIRMS) used to determine the ratio of $^{13}\text{CO}_2$ to $^{12}\text{CO}_2$ in breath samples.

3.4 Components and Pictures of ^{13}C -Spirulina GEBT Kit, Prepared Test Meal and ABCA GIRMS Instruments

The components of the ^{13}C -Spirulina GEBT are addressed below.

- ¹³C-Spirulina Gastric Emptying Breath Test (GEBT) – Test Meal (¹³C-Spirulina/Egg)

Ingredients: Desugared whole eggs, Dry non-fat milk solids, Salt, Smoke Flavoring (Char Oil), ¹³C-labeled Spirulina

Nutritional value: Fat 8.8 g; Carb 4 g; Fiber 0 g; Protein 12 g

Energy value: 150 kCal

Net weight: 27 g

- ¹³C-Spirulina Gastric Emptying Breath Test (GEBT) – Saltine Crackers (3 packages of 2 crackers)

Ingredients: Unbleached enriched wheat flour (wheat flour, niacin, reduced iron, thiamine mononitrate, riboflavin, folic acid), canola oil, palm oil, sea salt, malted barley flour, baking soda, yeast

Nutritional value: Fat 1 g; Carb 14 g; Fiber 0 g; Protein 1g

Energy value: 80 kCal

Net weight: 18g

- Overall Meal Nutritional/Energy Values

Fat 9.8 g; Carb 18 g; Fiber 0 g; Protein 13 g; 230 kCal

Table 1. Contents of ¹³C-Spirulina GEBT Kit

Meal preparation components of Kit	Breath Sample Collection Components of Kit
1 Instructions for Use/Package Insert	1 Test Request Form
1 ¹³ C-Spirulina/Egg Meal packaged in a foil pouch with oxygen absorber	2 Blue-Capped Exetainer tubes labeled for pre-meal collection
3 packages of 2 saltine crackers re-packaged in a foil pouch with oxygen absorber	6 White-Capped Exetainer tubes labeled for post-meal collection
1 large (~13 fl oz/390 mL) microwaveable cooking cup	2 drinking straws
1 filling cup (small (~3.5 fl oz/~100 mL) plastic cup with pour spout for transferring water)	1 Breath tube holder
1 plastic cutlery kit (knife, fork and spoon)	1 Pre-labeled Bubble Mailer

Figure 1. Contents of ^{13}C -Spirulina GEBT Kit Displayed

Figure 2. Prepared ^{13}C -Spirulina GEBT Test Meal and Breath Sample Collection Components

Figure 3. ABCA GIRMS instrument Approved by FDA for Use with GEBT

3.5 Summary of Relevant Clinical Studies

The GEBT was validated in FDA-approved dual-labeled validation studies. The comparative method was a nuclear medicine procedure known as Gastric Emptying Scintigraphy ("GES"). GES is conducted by administering a radionuclide-labeled test meal to a fasting patient and measuring the rate of radiation decline with time as the stomach empties the labeled test meal. In the validation studies GEBT and GES were conducted concurrently (Mayo Clinic). GEBT demonstrated excellent agreement with diagnosis by GEBT vs. GES.

The FDA approved GEBT for commercial use in April 2015 (Pre-Market Approval PMA P110015: Gastric Emptying Breath Test). Exhibit A includes the FDA's public announcement of the approval and a copy of PMA 110015 Gastric Emptying Breath Test Letter of Approval.

GEBT has an excellent safety profile with no serious adverse events reported in pre-validation, validation and post validation studies. There have been no medical device reportable (MDR) events post approval (> 5,000 GEBT).

A recent international consensus statement recommended GEBT for use in the evaluation of gastroparesis "because of its careful validation, high concordance with scintigraphic data and FDA approval" (INTERNATIONAL CONSENSUS STATEMENT: Advances in the diagnosis and classification of gastric and intestinal motility disorders. Gastroenterology and Hepatology, Volume 15, May 2018).

GEBT is currently used in the majority of Phase II, and III pharmaceutical studies for new drugs for gastroparesis. In these studies, GEBT is used to identify gastroparetic patients for enrollment and to assess physiologic effects of new pharmacologic agents (U.S. Department of Health and Human Services, Food and Drug Administration, Center for Drug Evaluation and Research (CDER); Gastroparesis: Clinical Evaluation of Drugs for Treatment; Guidance for Industry. July 2015, August 2019. Clinical/Medical).

Table 2 below summarizes key peer-reviewed literature regarding ¹³C-Spirulina GEBT.

Table 2. Summary of Key Peer-Reviewed Literature

Publication	Brief Description

J S Lee, M Camilleri, A R Zinsmeister, D Burton, L J Kost, P D Klein. A valid, accurate, office based non-radioactive test for gastric emptying of solids Gut 2000;46:768–773
	
Proof of principle study in healthy subjects showing the excellent correlation of simultaneous ¹³C-Spirulina GEBT measurements with GES.

4.0 STUDY GOALS AND OBJECTIVES

The purpose of this study is to establish the usability of a telehealth platform for the administration of GEBT. The objectives of this study are as follows:

- To demonstrate the safety of administering the ¹³C-Spirulina GEBT by telehealth by showing that there is no more than expected frequency of adverse events during administration of GEBT by a telehealth professional, than would be expected during administration of GEBT in a clinician's facility
- To demonstrate patient ability to prepare and administer the ¹³C-Spirulina GEBT, under the supervision of a telehealth professional, according to instructions
- To demonstrate patient ability to complete the GEBT test request form, under the supervision of a telehealth professional, according to instructions
- To demonstrate patient ability to collect GEBT breath samples under the supervision of a telehealth professional
- To demonstrate the ability to successfully ship kits/breath samples to/from home
- To demonstrate the ability of a telehealth platform to function correctly and be used correctly by virtually supervised patients

- **Note:** The steps and order of steps for tele-supervised GEBT administration is the same as that currently conducted in doctors' offices according to approved GEBT labeling.

5.0 SUBJECT SELECTION

Cairn personnel and their family and friends may volunteer to be a participant in this study provided they are not familiar with the GEBT test administration procedure and have never been administered a GEBT test.

Participants may also be recruited from gastroenterology, multi-disciplinary, primary care or clinical research practices knowledgeable and experienced in the evaluation and treatment of patients suspected of gastroparesis (intended use population for GEBT). Participants should not have previously undergone a gastric emptying breath test.

This study requires a minimum of thirty (30) and up to fifty (50) participants. Of the participants required for this study, at least fifteen (15) must be symptomatic for gastroparesis, at least fifteen (15) must be over the age of 55, and at least fifteen (15) must have no higher than a high school education or equivalent.

5.1 Inclusion criteria

Participants are eligible to be included in the study if they meet the following criteria:

- Males and females, ≥ 18 years of age at the time of signing the consent form, from healthy and intended use population (i.e. symptomatic for gastroparesis). Women of childbearing potential must not be pregnant at the time of GEBT administration.
- Ability to eat test meal and provide breath samples.
- Access to a microwave oven at home
- Internet connection and telehealth accessible device (smart phone/tablet/computer with visual and voice capability) at home
- Environment to sit comfortably and quietly at home.

5.2 Exclusion criteria

Participants are **not** eligible to be included in the study if they meet any of the following criteria:

- History or physical exam suggestive of systemic disease such as pathophysiologic disorders such as renal failure, chronic heart disease, chronic respiratory disease, liver disease, or malabsorption syndrome
- History of abdominal surgery except appendectomy
- Pregnancy

- Intolerance or allergy to any component of GEBT meal
- History of neurologic or psychiatric disorders

5.3 Participant Meal and Dietary Restrictions

The participant will fast for at least 8 hours (preferably overnight) prior to administration of the GEBT. Alcohol should not be consumed within 8 hours prior to testing. The participant may consume a small amount of water up to 1 hour before the test, but not more than 4 fl oz.

Subjects should not smoke/use tobacco products (e.g. chewing tobacco, nicotine gum) before or during administration of the GEBT.

5.4 Participant Activity Restrictions

The participant will abstain from strenuous activity for at least 8 hours prior to administration of the GEBT. Participants may participate in light activities during administration of the GEBT (e.g. watching television, reading, using restroom) but otherwise will remain comfortably seated in the test administration location.

6.0 STUDY PROCEDURES/RESEARCH METHOD

6.1 Study Scheme

Visit 1: For each potential participant, perform a screening visit at the clinical study site or via the telehealth communications platform where the study is explained to the participant. Ensure that the participant is eligible to participate in the study. Answer any questions about the GEBT test procedure and ask the participant to provide consent to participate in the study (see SPEC-CD-036). The informed consent form will be signed in the presence of the research coordinator explaining the consent form. A copy of the signed consent form will be sent via fax, scan or email for the research coordinator to sign and return to the participant. Participants are free to leave the facility or log out upon completion of the screening visit.

Visit 2: Within two weeks of visit 1, participants will log into the telehealth platform using the information provided by a Cairn telehealth administrator at which time the GEBT will be administered under virtual supervision. After confirmation that the participant has met the fasting and dietary restriction requirements, the participant will begin to complete the test request form, provide baseline (PRE-meal) breath samples, prepare the GEBT test meal, consume the prepared GEBT test meal, and collect post meal breath samples at 45, 90, 120, 150, 180 and 240 minutes after consumption of the meal under the supervision and instruction of a Cairn telehealth administrator.

Visit 3: Follow up contact (e.g. phone call, email, in-person, etc) will be made with the participant within one week following the GEBT administration to assess whether there were any post-administration adverse events and to administer a patient questionnaire to complete the subject's participation in the study.

Table 3. Schedule of Activities (SoA)

Procedure	Screening (Visit 1)	Visit 2	Follow-up (Visit 3)	Notes
Informed Consent	X			
Inclusion and exclusion criteria	X			
Telehealth administration of ¹³ C-Spirulina GEBT		X		
Completion of post-test questionnaire			X	
AE review			X	
SAE review			X	

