6.4.4 Participant Training

Participants in this study who are taking the GEBT at home, under supervision of a telehealth professional will receive no prior training in how to administer the GEBT, in the same way that patients that would be administered the GEBT via telehealth would not have had prior training. Telehealth administrators, who are Cairn employees, will be trained on telehealth administration procedures (SOP-CD-028, Exhibit E) according to standard Cairn training policies. A minimum of two and up to four different individuals trained in telehealth procedures will administer the GEBT by telehealth for this study.

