6.5.7 Ability of a telehealth platform to function correctly

There are no significant problems with the telehealth platform: majority of users find the telehealth platform to be simple to use and do not have issues with internet access.

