16.0 REVISION HISTORY

Revision Level	Brief Description of Revision(s)	Effective Date
00	Initial Document	11-05-2020
01	Updated section 6.1, visit 1 to include performing informed consent using telehealth platform and how to obtain a copy of the signed informed consent from the participant; Updated exclusion criteria to remove the exclusion of females on hormone replacement therapy other than birth control and receipt of investigational drugs; Updated Exhibit D, section 2.0 to add 180- and 240-minute time points to table	See first page of this document.

Principal Investigator Agreement:

By signing this protocol, I commit to conducting the clinical investigation in accordance with the procedure all requirements of the investigational plan, IDE regulations, other applicable regulations of the FDA, and any conditions of approval imposed by the Institutional Review Board (IRB) or FDA. I agree to abide by all of the responsibilities of investigators addressed in 21 CFR Part 812, Subpart E and Subpart G.

	NAME (Print)	SIGNATURE	DATE
Principal Investigator:	SEE	ATTACHED	SD 12/14/20

[figure not shown]
- B. Telehealth Administration of ^{13}C -Spirulina Gastric Emptying Breath Test (^{13}C -GEBT) Usability Study – Patient Questionnaire to be completed at end of ^{13}C -Spirulina GEBT
- C. Telehealth Administration of ^{13}C -Spirulina Gastric Emptying Breath Test (^{13}C -GEBT) Usability Study – Telehealth Administrator Patient Ability/Compliance Questionnaire
- D. Telehealth Administration of ^{13}C -Spirulina Gastric Emptying Breath Test (^{13}C -GEBT) Usability Study – Test Request Form and Breath Sample Evaluation
- E. SOP-CD-028, Telehealth Administration Procedures
- F. SPEC-CD-032, Patient Preparation Sheet

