6.0 REVISION HISTORY

Revision Level	Brief Description of Revision(s)	Effective Date
00	Initial revision.	See the first page of this document.

UNCONTROLLED COPY
Version May Not Be Current

CAIRN DIAGNOSTICS	DOC No. SOP-CD-028.00 EXHIBIT A
SOP: Telehealth Administration Procedures EXHIBIT A: PATIENT WELCOME CALL SCRIPT	Page 1 of 2

Welcome Call Script:

Phone call to patient after receiving Telehealth Physician Order Form

Good morning/afternoon. My name is "CSM/CSR Name" with Cairn Diagnostics, May I speak with Jane Doe?

[name], I am calling to schedule your Gastric Emptying Breath Test, AKA GEBT, ordered by Dr. _____. It will take about 5 minutes to schedule your procedure.

Great! To get started, I need to verify some information (*which is found on the Physician Order Form*). Please confirm your:

- Name
- DOB
- Shipping address for kit shipment
- Mobile phone number
- Email

The GEBT test will be conducted at your home using a secure video link. I need to ask you a few questions to be sure we are able to conduct the GEBT at your home under the direction of one of Cairn Diagnostic's tele-administrators. (*Record on the Telehealth Patient Contact Form, FORM-CD-036*)

1. Is your mobile phone able to send and receive text messages?
2. Do you have a Smartphone/tablet/iPad or laptop with audio/video capabilities and internet access at home? What device do you plan on using for the tele-administration of the GEBT? (*choices are smartphone, tablet, or laptop*)? (*Ask what device will be used and enter on the form*)
3. Do you have a microwave that you can use on the day of the test?
4. If you are an insulin dependent diabetic, will someone be able to accompany you, or check on you, during the test?
5. After the test is finished you will need to send your breath samples back to us in a prepaid bubble mailer, which will be included in the GEBT kit. We usually use UPS. Do you have access to a UPS store nearby or do you live in a building which offers UPS pickup? (*CSR may have look up the nearest UPS drop-off location <https://www.ups.com/dropoff/>. If UPS dropoff/pickup is not available, contact the shipping department for an alternative method.*)

(If the answer to questions 1-5 are all Yes, continue; if no to any one question, stop and reschedule.)

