Ok, now let's get you scheduled. You will need to set aside approximately 5 hours to complete the test. Our next available appointment is "Day, Date and Time of appointment" (e.g., Friday, August 3, 2020 at 7 am).

You will receive a text message confirming your appointment. You will also receive an email that will include the Telehealth GEBT Patient Preparation Sheet that **must be reviewed prior to the morning of the test. It will also be provided with your kit. There are certain items that you are required to have to complete the test that are not included in the test kit.** Within this

same email you will receive a link to our patient informational video which discusses what to expect when taking the GEBT at home.

Your GEBT Kit will be shipped to the address we confirmed earlier. You will receive an automated text when the kit has been shipped, which will include the tracking number and an approximate delivery date. We will send a follow-up text within 2 or 3 days to verify that you have received the kit.

The day before your test you will receive a text message reminder. **Please be sure to review the patient preparation sheet and the patient informational video!** Thank you for scheduling your test. Do you have any additional questions? (note any questions asked and answers given)

UNCONTROLLED COPY
Version May Not Be Current

CAIRN DIAGNOSTICS	DOC No. SOP-CD-028.00 EXHIBIT B
SOP: Telehealth Administration Procedures EXHIBIT B: TELEHEALTH ADMINISTRATION CALL SCRIPT	Page 1 of 8

Step	Tele-Administrator	Form Location	Notes
1	Good Morning, my name is (Tele-administrator Name), and I will be your tele-administrator for the GEBT. Before we start, I have a few things I need to confirm.		
2	Please verify your Name and Date of Birth. I also need to verify your identity. Would you show me a picture ID such as your driver's license, etc.?	Section 1 Question 1	Verify that the Name and DOB on the order form matches their answer. If it does not match write in the correct information on the form
3	Did you receive the GEBT Test Kit? Would you read to me or show me the barcode number on the right-hand side of the kit box?	Section 1 Question 2	This should have been confirmed ahead of time through shipping and patient text confirmation.
4	What is the kit lot number and expiration date that are printed on the label on the left hand side of the kit box?	Section 1 Question 3	If the kit has an expired lot number, do not proceed with the test

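### Screening and consent may take place on the telehealth platform whose ease of use is being tested, which gives some participants an extra session that intended users would not have

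*Protocol*

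**What the plan says.** Section 6.1 offers two routes for Visit 1: staff are to "perform a screening visit at the clinical study site or via the telehealth communications platform". The remote route is a live session, since "Participants are free to leave the facility or log out upon completion of the screening visit". The test itself follows at Visit 2: "Within two weeks of visit 1, participants will log into the telehealth platform using the information provided by a Cairn telehealth administrator". The revision history describes the change to Visit 1 as "Updated section 6.1, visit 1 to include performing informed consent using telehealth platform".

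Section 6.4.10 says the study will verify that the software is user friendly. The matching acceptance criterion, 6.5.7, asks that the "majority of users find the telehealth platform to be simple to use and do not have issues with internet access". The data on ease of use come from the video-link item in Exhibit B section 6 (answered by the patient) and the patient-trouble item in Exhibit C section 3 (answered by the telehealth administrator).

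For routine use, SOP-CD-028 section 3.3 and its Exhibit A make the first live contact a scheduling call: "Phone call to patient after receiving Telehealth Physician Order Form". The first video call comes on the day of the test (SOP-CD-028 section 3.5).

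**The concern.** The synopsis and section 6.4.1 say that the study deliberately includes older and less educated participants because they may be less familiar with technology. For them the informative observation is how they manage the platform when they first meet it, as a telehealth patient would on test day. A participant screened remotely has already logged in, held a conversation and logged out within the two weeks before Visit 2. The ease-of-use items then describe someone with more platform experience than the intended user, and the error favours passing.

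The protocol does not limit or record how many participants take the remote route. If the route is not captured elsewhere, the effect cannot be separated out afterwards.

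**Working it through.** **1. Platform contacts before and during the test**

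| | Before test day | Test day |
|---|---|---|
| Routine patient (SOP-CD-028) | Telephone call, texts, email | Initial and final video calls |
| Participant screened at the site (6.1) | No platform session required by 6.1 | Initial and final video calls |
| Participant screened remotely (6.1) | One platform session | Initial and final video calls |

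Only the third row departs from routine use, by one session.

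**2. Is it the same platform?** Section 6.1 does not name the Visit 1 product. It uses the term telehealth communications platform for Visit 1 and telehealth platform for Visit 2. The revision history uses the latter term for Visit 1 too. The natural reading is one platform, but this rests on shared wording.

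**3. Is there a safeguard?** Participants must be naïve to the GEBT (synopsis, 5.0, 6.4.2), but nothing requires them to be naïve to the platform. Exhibits B, C and D have no field for the Visit 1 route or earlier platform use. Section 6.5.7 is not split by route.

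**4. Size.** The protocol gives no rate for ease of use, no share screened remotely and no statistical derivation of the 30 to 50 participants, so there is no figure of its own to reproduce. What follows is an illustration. All rates are assumptions, responses are taken as independent, and only the ease-of-use half of 6.5.7 is modelled.

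Let p0 be the proportion of first-time users who find the platform simple, p1 the proportion among those with an earlier session, and s the share screened remotely. The observed rate has expectation

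p = (1 − s)·p0 + s·p1,

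and the majority rule is met with probability P(X ≥ r), where X is binomial(n, p), r = 16 for n = 30 and r = 26 for n = 50.

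With p1 = 0.70:

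| p0 | s | p | P(met), n=30 | P(met), n=50 |
|---|---|---|---|---|
| 0.40 | 0 | 0.40 | 0.097 | 0.057 |
| 0.40 | 0.5 | 0.55 | 0.645 | 0.716 |
| 0.40 | 1 | 0.70 | 0.983 | 0.998 |
| 0.50 | 0 | 0.50 | 0.428 | 0.444 |
| 0.50 | 0.5 | 0.60 | 0.825 | 0.902 |
| 0.60 | 0 | 0.60 | 0.825 | 0.902 |
| 0.60 | 0.5 | 0.65 | 0.935 | 0.979 |

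For example, with p0 = 0.40 and s = 0.5, p = 0.5 × 0.40 + 0.5 × 0.70 = 0.55.

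Now take p0 = 0.70 and p1 = 0.90, that is, trouble in 30% on first use and 10% after an earlier session. The expected trouble rate is 0.5 × 0.10 + 0.5 × 0.30 = 20% with half screened remotely, 0.8 × 0.10 + 0.2 × 0.30 = 14% with 80%, and 10% with all. The reported trouble rate falls by a third to two thirds. The verdict does not move, because the rule is already met with probability 0.983 (n=30) or 0.998 (n=50) at 70% ease.

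**The case against.** **The rule is lenient.** A majority suffices, and at 70% first-use ease it is almost certain to be met without any help. This stands. It limits the consequence for pass or fail, but not the distortion of the reported rate.

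**Everyone has two video calls at Visit 2.** Joining means selecting a texted link, and Exhibit B is answered after the test, so even a site-screened participant rates the link after two uses. That is true, but a routine patient would be in the same position. The extra session remains a difference. The objection does narrow the point: the texting item and the lost-connection items are not obviously improved by an earlier session, and the meal, form and breath-sample criteria are not directly affected.

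**Sections 6.4.2 and 6.4.4 are not breached.** A reader might infer that remote screening contradicts the rule that participants "will receive no prior training in how to administer the GEBT, in the same way that patients" would not. It does not. That rule and the single-occasion rationale concern the GEBT, and neither promises platform-naïve users. The tension is with the aim of testing people unfamiliar with the technology, not with an explicit rule.

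**Pre-selection.** A reader might also infer that anyone unable to connect at a remote Visit 1 is lost, leaving only successful users. The documents do not support that as a certainty. The site is an alternative route, no rule excludes a person for a failed connection, and section 5.1 requires an internet connection and a suitable device on either route.

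**Informational video.** It might seem that the video sent before the test is a further source of bias. SOP-CD-028 sends it to routine telehealth patients as well, so it matches intended use.

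**Conclusion.** The point holds as a modest bias in one criterion. Section 6.1 permits an extra platform session that the routine pathway does not contain, no supplied form records who had it, and it can make the ease-of-use items behind 6.5.7 look better than for first-time users. The size cannot be determined from the documents, since the share screened remotely may lie anywhere from 0 to 100% and no rates are given. The majority verdict is at risk only if true first-use ease is near or below 50%. Above that, the effect is confined mainly to the reported rate. The conclusion assumes that Visit 1 and Visit 2 use the same platform, and that one earlier session makes the next one easier.

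**What to change.** In section 6.1, hold remote screening and consent on a channel other than the study platform.

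If the platform is used for Visit 1:

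- record the Visit 1 route for each participant;
- report 6.5.7 overall and separately for participants whose first platform use is Visit 2;
- base the ease-of-use conclusion on the latter group where numbers allow.

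Failed Visit 1 connections may be tallied descriptively, without identifying data. They should not be scored under 6.5.7, because the people concerned may not have consented and section 12.2 requires signed consent before any study activity.

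The cost is a sentence or two of protocol wording and one data field. The downside is either a second channel for consent or a first-use subgroup that is smaller than the full 30 to 50 and could be very small if most screening is remote. That is a reason to prefer the separate channel.
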